**CANVAS Trial (AFT-28) Synopsis**

Study Title	Direct Oral Anticoagulants (DOACs) versus LMWH +/- Warfarin for VTE in Cancer: A Randomized Effectiveness Trial (CANVAS Trial)
Study Number	AFT-28
Sponsor	Alliance Foundation Trials, LLC (AFT)
Funding	This trial is supported through a Patient-Centered Outcomes Research Institute (PCORI) Award (CER-1503-29805).
Study Type/Phase	Randomized Effectiveness Trial
Clinical Indication	VTE (venous thromboembolism) associated with cancer
ClinicalTrials.gov Identifier	NCT02744092
IND Number	None, no IND
Number of Trial Patients	811 study-wide ( Note: This is the final N. )
Estimated Duration of Trial	3.5 years
Acronyms used throughout the protocol	
AFT - Alliance Foundation Trials, LLC
 
VTE - Venous Thromboembolism
 
DVT - Deep Vein Thrombosis
 
PE - Pulmonary Embolism
 
LMWH - Low Molecular Weight Heparin
 
DOAC - Direct Oral Anticoagulants

Rationale	Cancer patients are at risk for VTE (venous thromboembolism). Anticoagulation therapy is necessary to prevent recurrent VTE . Current practice patterns are a hybrid use of LMWH+/-warfarin. Recently, the FDA has approved 4 Direct Oral Anticoagulants (DOACs) for VTE based on efficacy trials showing non-inferiority to warfarin. Given the myriad exclusion criteria present in efficacy trials, the effectiveness of DOACs in cancer is unknown .
Objectives	
Objective 1: To compare the effectiveness of anticoagulation with a DOAC (intervention) with LMWH/warfarin (comparator) for preventing VTE recurrence in patients with cancer.
 
Objective 2: To compare the harms of DOAC vs. LMWH/warfarin therapy for cancer patients with VTE based on the cumulative rate of major bleeding at 6 months.
 
Objective 3: To compare the impact of DOAC vs. LMWH/warfarin therapy on the experience and burden of anticoagulation therapy for cancer patients with VTE.
 
Objective 4: To compare the impact of DOAC vs. LMWH/warfarin therapy on mortality in cancer patients with VTE.

Trial Design	
The study design is a randomized effectiveness study to evaluate the effectiveness of DOAC therapy compared to usual care with LMWH/warfarin. Participants who decline randomization will be offered the opportunity to participate in the preference cohort.** This is a hybrid design that consists of both a randomized cohort and a preference cohort.** Eligible patients who accept randomization will be enrolled in the study (the randomized cohort), and they will be randomly assigned to either the DOAC therapy group (Arm 1) or the usual care group (Arm 2).** Those patients who decline randomization but choose treatment on one of the two study arms (Arm 1 or Arm 2) will be enrolled to the study (the preference cohort).** See the “Statistical Considerations” section of this protocol for complete details.
 
**The randomized cohort closed to new enrollment in April, 2020. Based on the results of monthly data monitoring performed June 2017, the preference cohort is CLOSED to new enrollment following the closing rule specified in the protocol.**

Eligibilty Criteria	Can be found here: 4.0 Patient Selection / Eligibility Criteria
Protocol Treatment	
Arm 1: Intervention arm, DOAC      Arm 2: Usual care, LMWH/warfarin
 
This effectiveness study will not provide any drugs because all drugs are commercially available, FDA-approved, and are being prescribed on-label. Drugs should be billed to the patient's insurance company or to the patient as your site does for any other standard medication. Drugs should be prescribed to the patient as your site does for any other standard medication.

## 1.0 BACKGROUND

**Venous Thromboemboli (VTE) are common, often lethal and a major public health threat** A deep venous thrombosis (DVT) is a blood clot in a large vein, usually in the leg or pelvis. Patients often note swelling, pain or redness in one leg. Sometimes a DVT detaches from its site of formation and mobilizes in the blood stream. If the clot travels through the heart to the lungs, it can suddenly block an artery supplying the lungs. This event is called a pulmonary embolism (PE). PE symptoms include shortness of

breath, chest pain, and rapid heart rate. Each year in the US, an estimated 600,000–900,000 people develop VTE, and more than 100,000 die, many suddenly. Because people who survive a first VTE are at extremely high risk for another episode, a main treatment goal is to prevent a second event.

**Multiple pathophysiologic mechanisms put cancer patients at excess risk for VTE** A cancer diagnosis is one of the strongest predisposing risks for VTE. VTE is sometimes the first manifestation of cancer. The excess VTE risk in cancer stems from three interrelated pathogenic mechanisms: 1) hypercoagulability; 2) stasis or slow blood flow; and 3) vascular injury to blood vessel walls. Tumor features such as histology (adenocarcinoma), site (pancreatic, kidney, uterus) and extent of disease increase risk. Certain chemotherapy agents, hormonal therapy, the use of indwelling catheters, surgery, hospitalization and immobility all increase risk and contribute to the high frequency of VTE in cancer patients.

**VTE is a frequent distressing complication of cancer and is associated with high mortality** Two population-based case control studies demonstrate that cancer increases the risk for VTE by 4 to 7 times and is the second leading cause of death in oncology patients. Approximately 20% of all VTEs occur in cancer patients. A recent study showed that 12.5% of chemotherapy recipients in ambulatory practice developed a VTE within 12 months. The rate varied from 8% to 19% depending on cancer type. In contrast, the VTE rate was only 1.4% for age and gender matched cancer-free controls from these practices. Cancer patients with VTE have more advanced disease, worse performance status and higher risk of death. Although much of the excess is due to cancer itself, a significant proportion is due to recurrent VTE.

**Anticoagulation therapy is necessary to prevent recurrent VTE** Cancer patients face very high risks of recurrent VTE particularly if they have high tumor burden or are receiving chemotherapy. Therefore, absent a major contraindication such as ongoing/active bleeding, very low platelet count, and/or large brain metastases, anticoagulation is indicated for cancer patients following VTE. This is true whether the VTE is symptomatic or an incidental finding detected on an imaging study. Practice guidelines recommend that advanced cancer patients continue anticoagulant therapy long-term since the risk of VTE persists indefinitely.

**Warfarin is the mainstay of anticoagulation treatment to prevent VTE but requires close monitoring** Warfarin is an oral medication often known by its brand name, Coumadin. It prevents the formation of blood clots and their migration. The FDA approved it in 1954 when found to prevent blood clots, and its use remains ubiquitous. Despite its effectiveness, treatment with warfarin has major shortcomings. Its therapeutic window is narrow. Too little warfarin fails to protect against VTE. Too much leads to an excess risk of bleeding. There is great variability in its metabolism, and it interacts with some foods and many medications. Therefore, close monitoring is required. This entails blood testing, often weekly, to ensure that the international normalized ratio (INR) is within therapeutic range. Warfarin therapy is especially challenging for cancer patients for two reasons. First, cancer patients take many medications which can either accelerate or impede warfarin metabolism. Second, warfarin has to be reversed prior to surgical procedures. This takes about 5 days and requires multiple blood draws.

**Low Molecular Weight Heparins (LMWHs) Are the Guideline Sanctioned Approach for Treating VTE in Cancer** For many years, the management of VTE consisted of several days of inpatient treatment with intravenous heparin followed by transition to oral warfarin. Because of unfractionated heparin's short half-life and metabolism, it required close monitoring and intravenous treatment. In the 1990s, the LMWHs (e.g., dalteparin (Fragmin) and enoxaparin (Lovenox)) were developed. They require subcutaneous injection but no blood monitoring. In 2003, the CLOT study demonstrated that in patients with malignancy and VTE, dalteparin was more effective than warfarin at reducing VTE recurrence (LMWH: 9%, warfarin: 17%) with similar bleeding rates. On this basis, LMWH therapy became the

preferred regimen. A Cochrane review of anticoagulation to prevent recurrent VTE in cancer found that recurrent VTE hazard was 0.47 (95% CI 0.32-0.71) for LMWH vs. warfarin with no major differences in bleeding, survival or other complications.

### **Anticoagulation therapy with either LMWH or warfarin is complex and often burdensome**

Notwithstanding its superior efficacy to warfarin and guideline endorsements, adherence to LMWH therapy is challenging because it requires daily injections. Patients encounter problems preparing syringes, injecting needles and with bruising. In order to undergo surgical procedures including biopsy, endoscopy, or catheterization, warfarin must be stopped a week in advance. To prevent VTE during this period, oncologists prescribe “a LMWH bridge” since LMWH has shorter half-life. After procedures are complete, warfarin can be restarted and LMWH discontinued when warfarin again reaches therapeutic levels, typically after 5 days. Analyses of practice patterns suggest that among cancer patients with VTE: about a third choose LMWH, a third warfarin, and a third opt for LMWH but transition to warfarin within several months when injections become too burdensome. Current oncology practice is thus best described as a *hybrid* strategy.

### **Direct Oral AntiCoagulants (DOACs) have recently been FDA approved to treat/prevent VTE**

DOACs (**Table 1**) are a major, recent therapeutic advance for management of VTEs. They are oral but unlike warfarin, do not require intensive monitoring to stay within therapeutic range. Four DOACS have recently been FDA approved. Factor Xa activates prothrombin to thrombin and triggers the coagulation cascade to form clot. Thrombin cleaves fibrinogen to fibrin, forming the structure of the clot. Apixaban, edoxaban, and rivaroxaban, directly inhibit Xa. Dabigatran directly inhibits thrombin. The DOACs were first approved to prevent stroke and embolism in atrial fibrillation and after orthopedic surgery. Each agent has been evaluated in large efficacy trials and shown to be at least as efficacious as warfarin at preventing recurrent VTE and at least as safe in terms of the risk of bleeding.

Table 1 Comparison of DOACs Recently Approved by the FDA				
Direct Oral Anticoagulants (DOACs)	Dabigatran  (Pradaxa)	Rivaroxaban  (Xarelto)	Apixaban  (Eliquis)	Edoxaban  (Savaysa)
FDA approval date for VTE	April 7, 2014	Nov 2, 2012	Aug 21, 2014	Jan 8, 2015
Target factor	II (thrombin)	Xa	Xa	Xa
Renal clearance	80 %	33 %	25 %	35 %
Renal dose modification	Don't use	Not if CrCl<30ml/min	None	30mg if CrCl<50
Hepatic metabolism	Minimal	Yes, CYP3A4	Yes, CYP3A4	Minimal
Liver failure modification	None	Don't use	Don't use	None
Bleeding risk vs. warfarin	same	same/better	better	better

**Efficacy trials have evaluated benefits/harms of DOACs for VTE in carefully selected patient groups** Table 2 summarizes the large efficacy RCTs comparing the DOACs to a vitamin K antagonist (VKA) (e.g., warfarin). Each demonstrates that VTE recurrence, bleeding and death rates from anticoagulation with a DOAC are non-inferior to rates with VKA. They led the FDA to approve the DOACs for VTE treatment. *Table 2 underscores how few cancer patients were included in these pivotal trials.* A recent meta-analysis showed similar findings for cancer subgroups. For example, the OR for VTE was 0.56 (95% CI 0.27-1.14) for DOAC vs. VKA therapy. Notably, these trials excluded patients with short life expectancy and significant

comorbidities, and in some trials, patients were excluded if they were eligible for treatment with LMWH. As a result of this evidence gap, it is not surprising that practice guidelines from the National Comprehensive Cancer Network, the American Society of Clinical Oncology, The European Society of Medical Oncology, The American Society of Hematology and the American Thoracic Society advocate neither for nor against DOAC use in cancer. These guidelines all emphasize the need for effectiveness studies and do not definitely recommend for or against use of DOACs versus LMWH/VKA therapy.

Table 2: Recent Large RCTs of DOACs vs. Warfarin Have Included Very Few Cancer Patients							
RCT Name	Intervention	Control	N	Cancer N (%)	Overall Outcomes: Intervention vs. Control		
					VTE/VTE death	Bleeding/Bleeding death	Any death
Amplify 	Apixaban	VKA	5395	169 (3%)	1.5 vs. 1.9%	4.3 vs. 9.7%	1.5 vs. 1.9%
Einstein-DVT 	Rivaroxaban	VKA	3449	207 (6%)	2.1 vs. 3.0%	8.1 vs. 8.1%	2.2 vs. 2.9%
Einstein-PE 	Rivaroxaban	VKA	4832	223 (4%)	2.1 vs. 1.8%	10.3 vs 11.4%	2.4 vs. 2.1%
HOKUSAI 	Edoxaban	VKA	8240	208 (2%)	3.2 vs. 3.5%	8.5 vs. 10.3%	3.2 vs 3.1%
RE-COVER I 	Dabigatran	VKA	2539	121 (5%)	2.4 vs. 2.1%	1.6 vs. 1.9%	1.6 vs. 1.7%
RE-COVER II 	Dabigatran	VKA	2589	100 (4%)	2.3 vs. 2.2%	1.2 vs. 1.7%	2.0 vs. 1.9%

\*AMPLIFY and RE-COVER I & II outcomes are event rates at 6 months; the other study outcomes reflect rates at 12 months

With this background, the rationale for this study is compelling because:

- VTEs occur commonly in cancer patients, can be fatal, and require anticoagulation to prevent recurrence.
- Warfarin has long been the mainstay of VTE treatment but requires careful blood monitoring.
- LMWHs are an alternative but require subcutaneous injection and thus are onerous for patients.
- LMWH prevents recurrent VTE in cancer better than warfarin in some studies but isn't clearly better in terms of safety or survival.
- Longstanding usual practice is a hybrid of LMWH/warfarin with many patients transitioning back and forth between the two. Typically, patients start on a LMWH and transition to warfarin; however, some stay on LMWH for the long term and may transition to warfarin at a later date particularly if chronic self-administration of subcutaneous injections becomes arduous.
- FDA has approved 4 DOACs for VTE based on *efficacy* trials showing non-inferiority to warfarin. These trials have included very few cancer patients leaving an evidence gap.
- Given the myriad exclusion criteria present in efficacy trials, the *effectiveness* of DOACs in cancer is unknown.

## 2.0 OBJECTIVES

Cancer patients are frequently diagnosed with VTE and need to choose an anticoagulation strategy. Although there are now multiple options, patients and their doctors lack information that clearly balances benefits/harms and burdens so as to inform these choices. To fill this gap, the proposed study has the following goals:

**Objective 1:** To compare the effectiveness of anticoagulation with a DOAC (intervention) with LMWH/warfarin (comparator) for preventing VTE recurrence in patients with cancer.

Hypothesis: The benefit of secondary prophylactic anticoagulation with a DOAC is not worse than the benefit from treatment with LMWH/warfarin based on cumulative VTE recurrence reported by patients or their clinicians at 6 months.

**Objective 2:** To compare the harms of DOAC vs. LMWH/warfarin therapy for cancer patients with VTE based on the cumulative rate of major bleeding at 6 months.

Hypothesis: The harms from DOAC therapy are not worse than the harms from LMWH/warfarin therapy based on the cumulative rates of major bleeding reported by patients or clinicians at 6 months.

**Objective 3:** To compare the impact of DOAC vs. LMWH/warfarin therapy on the experience and burden of anticoagulation therapy for cancer patients with VTE.

Hypothesis 3a: DOAC and LMWH/warfarin therapy are associated with similar overall HRQOL (health-related quality of life) at 3 and 6 months.

Hypothesis 3b: DOAC therapy is superior to LMWH/warfarin based on the Anti-Clot Therapy Scale at 3 and 6 months.

**Objective 4:** To compare the impact of DOAC vs. LMWH/warfarin therapy on mortality in cancer patients with VTE

Hypothesis: The risks of all cause and cause-specific mortality for cancer patients treated with DOAC therapy are not worse than the risks for those treated with LMWH/warfarin based on survival at 6 months.

## 3.0 STUDY DESIGN

### 3.1 Description of study and schema

The study design is a **prospective unblinded two-group randomized effectiveness study** to evaluate the effectiveness of DOAC therapy compared to the usual care with LMWH/warfarin. The study has a hybrid design in that in addition to the randomized cohort, it also includes a preference cohort.\*\* Eligible patients who accept randomization will be enrolled in the study (**the randomized cohort**), and they will be randomly assigned to either the DOAC therapy group (Arm 1) or the usual care group (Arm 2).\*\* Those patients who decline randomization but choose treatment on one of the two study arms (Arm 1 or Arm 2) will be enrolled to the study (**the preference cohort**).\*\* See protocol section **13.0 Statistical Considerations and 18.0 Statistical Analysis Plan** for complete details.

The study intervention, DOAC therapy, has established *efficacy*, but its real world effectiveness in cancer patients is unknown. The study outcomes are measurable and meaningful to patients and their families. Knowledge from this study will help patients and their clinicians make better informed decisions about anticoagulation therapy. To understand the impact of individuals who choose not to be randomized, the study will also track outcomes for patients who consent to report outcomes, but decline randomization.\*\* This hybrid design as well as a well-specified plan for capturing important patient and treatment factors will enable better understanding of the relative risks/harms for individuals with specific features.

**\*\*The randomized cohort CLOSED to new enrollment in April, 2020. The preference cohort is CLOSED to new enrollment.**

The protocol schema can be found above.

### 3.2 Study Completion

The anticipated study completion date (the date by which the last data point for final data analysis is received) is November 15th, 2020. This presumes that no patients are enrolled after May 1st and that 6 month follow up data is complete as of November 1st. Two extra weeks have been added in case it should be necessary to track late assessments. Please note: the official study completion date will be dependent on the date of the last enrolled patient.

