## 8.6 Follow-up Study Questionnaires

The **Follow-up Study Questionnaire** (administered at 3-months post-enrollment and again at 6-months post enrollment) will collect: patient-reported ECOG performance status, SF-12 HR-QOL, anticoagulation therapy information including dose and adherence, ACTS anticoagulation

therapy burden (the Anti-Clot Treatment Scale (ACTS) is a 15-item patient-reported instrument of satisfaction with anticoagulant treatment), VTE recurrence, and bleeding.

It is the **Central Study Coordinator's responsibility** to administer the Follow-up Study Questionnaires to the participant.

**Timing:** The Follow-up Study Questionnaire will be administered once at 3-months (+/- 1 month) after enrollment and once at 6-months (+/- 1 month) after enrollment.

- If a participant has withdrawn consent to participate in the patient questionnaire component of this study, then do not administer any additional Follow-up Study Questionnaires.

The **Central Study Coordinator** will contact the participant via phone, internet, and/or postal mail depending on participant preferences.

- To administer the questionnaire via SECURE WEBLINK: The Central Study Coordinator will email the secure, individualized questionnaire link to the participant. The participant will enter his/her responses directly into REDCap using the link provided.
- To administer the questionnaire via PHONE: The Central Study Coordinator will follow the phone script found in Appendix: Follow-up Study Questionnaire – for administration via phone". The Central Study Coordinator will enter the participant's responses into REDCap.
- To administer the questionnaire via POSTAL MAIL: The Central Study Coordinator will print and mail the paper version of the Follow-up Study Questionnaire along with a prepaid return envelope to the participant's mailing address. The Central Study Coordinator will enter the participant's responses into REDCap, and keep the original paper copy in the participant's central study file.

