## 13.6 Toxicity

Using the AFT mechanism, we will monitor reportable adverse events every month during the study. Every month, the study chair and the study statistician will determine if further review by the study team and the DMSB is necessary.

In particular, we will monitor the adverse event rates of 1) thrombosis, 2) bleeding and 3) all-cause of mortality. If a statistically significant difference in any of these adverse events is observed at any time during the study, the DMSB will consider recommending the termination or modification of the study from safety perspective.

Toxicity event rates will be compared between DOAC and LMWH/warfarin, using Fisher's exact test. Please see section 13.5 for evaluation of bleeding risk and categorization of bleeding events.

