**RECORDS ON REVISIONS**

Version	Date for creation or modification	Person in charge	Remarks
Ver. 1	December 15, 2020	[name]	Originally prepared
Ver. 2	January 25, 2021	[name]	Updated

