### Modified Intention-to-Treat (ITT) population (Primary analyses)

Based on the data review performed before conducting the final analysis, we found that quite a few subjects in this pragmatic trial did not receive treatment according to their assigned group. In the ITT population, those patients who received treatment in the group opposite to the one to which they were randomized would also be included in the analysis. Based on the concern that these subjects could cause a potential bias toward the noninferiority claim with the ITT analysis, we have defined a modified ITT population. In order to be conservative with regard to testing the non-inferiority hypothesis, the primary analyses will rely on the modified ITT population. The modified ITT population includes all subjects who received a study drug according to their assigned treatment group and participated in this study.

The modified ITT population for the randomized cohort includes all randomized subjects who received at least one dose of the anti-coagulation treatment strategy to which they were assigned. The preference modified ITT population includes all non-randomized subjects who received the anti-coagulation treatment which they preferred subsequent to informed consent to study participation. The full modified ITT population includes the sum of the two aforementioned categories (randomized cohort and preference cohort).

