### 3.5.2.2. *Planned Interim Analyses*

This study design incorporates several interim analyses and one final analysis for the comparison of the primary endpoint. A 90% two-sided repeated confidence interval (RCI) for the difference in the cumulative incidence rate of VTE at 6 months (DOAC minus Usual Care) between two arms was estimated. We use the critical values based on the Lan-DeMets error spending function corresponding to the truncated version of O'Brien-Fleming boundaries.

Prior to the final analysis, four interim analyses were conducted on September 7, 2018, March 22, 2019, September 9, 2019, and March 25, 2020. Given these interim analyses, the critical value for the final analysis will be 1.710, which corresponds to a one-sided 0.0436 alpha. The confidence coefficient of the 90% two-sided RCI will be 91.28% for the final analysis.

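### Noninferiority is decided only in a post-randomisation subset (modified ITT), defined from an undated data review in a SAP first prepared after the anticipated last data point, and ITT has no decision role

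*Combined protocol and SAP*

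**What the plan says.** - **Design.** Protocol 3.1 describes a "prospective unblinded two-group randomized effectiveness study".
- **End of data.** Protocol 3.2 gives the anticipated date in these words: "the date by which the last data point for final data analysis is received) is November 15" (2020). It adds that "the official study completion date will be dependent on the date of the last enrolled patient". Protocol 8.6 allows the last questionnaire "once at 6-months (+/- 1 month) after enrollment".
- **SAP dates.** The SAP revision record dates version 1, marked as the original preparation, "December 15, 2020". Version 2, the current text, is dated 25 January 2021.
- **Origin of the primary set.** SAP 3.2 begins its account of modified ITT with "Based on the data review performed before conducting the final analysis, we found that quite a few subjects in this pragmatic trial", and says that these patients were not treated according to their assigned group. It fears that patients treated in the opposite group would bias ITT toward noninferiority, and makes modified ITT primary in order to be conservative. In the randomised cohort the set needs at least one dose of the assigned strategy.
- **Decision rule.** Protocol 13.3.1 and SAP 3.5.2.1 apply the 3% margin in the randomised modified ITT set only. SAP 3.5.2.2 sets the final critical value at 1.710 (one-sided 0.0436, a 91.28% interval).
- **Role of ITT.** Protocol 8.9, protocol 13.3.3(6) and SAP 3.5.2.3(6) make ITT a sensitivity analysis. No rule covers a disagreement between the sets.

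**The concern.** ITT is fixed by randomisation. Modified ITT depends on what happened afterwards, and its definition is documented only after follow-up was due to end. The SAP gives neither the date of the review, nor what its authors could see, nor how many patients the definition removes from each arm. If the two sets disagree, the plan as written claims noninferiority from the later-defined one.

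The protocol's own rules show how exclusion could be linked to outcome. The endpoint clock starts at enrolment (SAP 3.5.1), protocol treatment may start up to 14 days later (protocol 11.2), and sites may leave the assigned drug after a recurrence (protocol 12.6). A DOAC-arm patient who recurs on LMWH before any DOAC dose might never take one, and would then leave the set together with the event. This is an inference from the rules; the documents give no counts. Early refusal of injections could remove patients from the other arm, so the net direction is unknown.

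**Working it through.** **1. Dates.** 15 November to 15 December 2020 is 30 days, and to 25 January 2021 it is 71 days. If the last patient enrolled on 1 May 2020 and used the whole extra month, the window closes on 1 December, and version 1 is still 14 days later.

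**2. The plan's alpha.** 1 − Φ(1.710) = 0.0436, and 1 − 2 × 0.0436 = 91.28%. Both stated figures reproduce.

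**3. Upper illustration: free choice between two sets.** Assume that the true difference is at the margin in both sets, and that the two z-statistics have correlation ρ = √f, where f is the fraction kept (assumed). The error is 1 − Φ₂(1.710, 1.710; ρ).

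| f | ρ | One-sided error |
|---|---|---|
| 0.95 | 0.975 | 0.052 |
| 0.90 | 0.949 | 0.055 |
| 0.85 | 0.922 | 0.058 |

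**4. Modified ITT can err.** Assume 335 per arm and true ITT rates of 10.5% (DOAC) and 7.5%, which is exactly at the margin. Drop a share x of the DOAC arm only, with event rate r among those dropped. The remaining DOAC rate is (0.105 − x·r)/(1 − x), d is that rate minus 0.075, and P(claim) = Φ((0.03 − d)/SE − 1.710).

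| x | r | d | SE | P(claim) |
|---|---|---|---|---|
| 5% | 20% | 0.0250 | 0.0221 | 0.069 |
| 5% | 30% | 0.0197 | 0.0218 | 0.108 |
| 10% | 20% | 0.0194 | 0.0222 | 0.109 |
| 10% | 30% | 0.0083 | 0.0215 | 0.242 |

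Selective loss from the control arm would move the estimate the other way.

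**5. ITT can err too.** Assume a true on-treatment difference of 3 points (10.5% against 7.5%) and a share c crossing over in each arm. The ITT difference is 0.03(1 − 2c). For c = 5% it is 0.027 and the error is 0.058. For c = 10% it is 0.024 and the error is 0.075. This is the bias that the SAP fears.

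**6. Power cost of requiring both sets.** The stated CI length of 6.1 points gives SE = 6.1/(2 × 1.645) = 1.854 points. A noninferiority power of 0.900 at 1.645 then implies a DOAC benefit of (1.282 + 1.645) × 1.854 − 3 = 2.43 points. That benefit gives superiority power Φ(2.43/1.854 − 1.645) = 0.37, while the same table states 0.756. The scenario behind the 0.900 therefore cannot be recovered, and the figures below are assumptions. They use 1.710, SE/√f for modified ITT and ρ = √f. In the crossover columns the ITT benefit is 2.43(1 − 2c) with c = 1 − f.

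| f | Modified ITT alone | Both, equal effect | Loss (points) | Both, crossovers | Loss (points) |
|---|---|---|---|---|---|
| 0.95 | 0.873 | 0.862 | 1.1 | 0.847 | 2.6 |
| 0.90 | 0.857 | 0.843 | 1.4 | 0.811 | 4.6 |

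**The case against.** The strongest reply is that the SAP gives a sound reason. Crossovers dilute ITT, step 5 confirms that this can inflate the error, and the change was meant to make the claim harder. The review is placed before the final analysis, and what it is said to have found concerns treatment received. ITT and per-protocol results will be reported, a CONSORT diagram is planned, and adjudication is masked (protocol 13.10), so a conflict would be visible. All of this stands. But masked adjudication protects event classification, not the choice of set, and a visible conflict still has no rule.

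Some stronger readings are tempting but not supported:

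- *Outcomes by arm guided the choice.* The documents show an unblinded trial and late dates, not use of outcomes. The November date is anticipated, and no lock date is given.
- *The monthly safety review showed the chair and statistician results by arm.* Protocol 13.6 says "Every month, the study chair and the study statistician will determine if further review by the study team and the DMSB is necessary". The comparison between arms is a separate sentence with no stated timing or audience.
- *The interim looks used another set, so 1.710 does not apply.* SAP 3.5.2.2 says "four interim analyses were conducted on September 7, 2018, March 22, 2019, September 9, 2019, and March 25, 2020" but does not name their population. Protocol 13.9 assigns review of formal interim analyses to the DSMB.
- *A few dropped DOAC events would settle the result.* Dropping four with their patients, from an assumed 17 to 27 among 335, moves the difference by about −1.1 points. Dropping four control events moves it by about +1.1. At assumed event rates of 5% to 8%, excluding 5% to 10% of 335 patients removes only about 0.8 to 2.7 events (16.75 × 0.05 to 33.5 × 0.08).

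Adding a two-set rule now is itself a late change, but it can only make noninferiority harder to claim.

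**Conclusion.** The point holds as a gap in protection, not as evidence of a choice driven by results. One subset, conditioned on treatment received and first documented after the anticipated end of data, carries the noninferiority conclusion alone. The conservative motive is credible, but it answers only one direction of bias.

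The 5.2% to 5.8% is an upper illustration for this kind of choice, because the plan names one set. Selective exclusion could do more (0.069 to 0.242 in step 4), but those figures assume one-sided loss and high event rates among the excluded. ITT alone could run at 0.058 to 0.075 under assumed crossover. Every exclusion share, crossover share and event rate is assumed, since the documents give no counts. Requiring both sets holds the final-look error at or below 0.0436 whenever the true difference in either set is at the margin, whatever their correlation.

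**What to change.** - **SAP 3.5.2.1(1) and protocol 13.3.1(1):** conclude noninferiority only if the upper bound of the final repeated CI is below 3% in both the randomised ITT set and the randomised modified ITT set. Name the 91.28% interval there, because these sections now say 90%.
- **SAP 3.2:** state when modified ITT was defined relative to the end of follow-up, and whether the data review was masked to outcomes by arm.
- **Reporting:** give, by arm, the patients whom modified ITT excludes and their recurrences.

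Both analyses are already planned, and protocol 8.9 already requires follow-up of patients who never receive the intervention, so only wording changes. The price is the power loss in step 6: roughly 1 to 1.5 points if the effect is the same in both sets, and about 2.5 to 4.5 points if 5% to 10% per arm are crossovers.
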